### **Date and Time of Onset**

The date of onset is the date when the first sign(s) or symptom(s) were first noted. If the AE is an abnormal clinically significant laboratory test or outcome of an examination, the onset date is the date the sample was taken or the examination was performed.

---

a Exception: if an AE with onset before the first IMP administration (i.e., a pre-treatment AE) changes in intensity, this must be recorded as 2 separate events. The initial AE should be recorded with outcome “not yet recovered” and the date and time of outcome are when the intensity changed. The second AE should be recorded with date and time of onset when the intensity changed.

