### **STATISTICAL METHODS (Continued)**

**Safety:** The safety analyses will be based on all subjects who receive at least 1 dose of IMP. All adverse events will be coded by system organ class and preferred term using the most current version of the Medical Dictionary for Regulatory Activities (MedDRA). A treatment-emergent adverse event will be defined as any adverse event occurring after the start of IMP or pre-existing medical condition that worsens in intensity after the start of IMP.

Clinical laboratory variables will be presented in 2 ways. First, mean change from baseline to the end of the double-blind treatment visit will be summarized. Baseline will be defined as the last assessment before the first dose of IMP. Second, the number and percentage of subjects with treatment-emergent potentially clinically significant laboratory values on or before the end of the double-blind treatment visit will be tabulated.

Other safety assessments will also be summarized descriptively.

Similar safety data summaries will be made for the open-label treatment period data.

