### **Adverse Events**

Adverse events should be recorded as diagnoses, if available. If not, separate signs and symptoms should be recorded. One diagnosis/symptom should be entered per record.

If a subject suffers from the same AE more than once and the subject recovers between the events, the AEs should be recorded separately. If an AE changes in intensity, a worst-case approach should be used when recording the event, i.e. the highest intensity and the longest duration of the event.a

A procedure is not an AE; the reason for conducting the procedure is. Hospitalization is not an AE; the reason for hospitalization is. Death is not an AE, but the cause of death is (an exception is sudden death of unknown cause, which is an AE).

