10.2 Adverse Events

Adverse events (AEs) will be classified according to the MedDRA version 17.1 or later.

Written narratives will be issued for all serious AEs (including deaths) and AEs leading to discontinuation.

A 'pre-treatment' AE will be defined as an AE that occurs between screening and the first dose of the IMP. A 'treatment-emergent AE (TEAE)' will be an AE which occurs in the time interval from initial dosing (IMP intake) to the end of treatment visit. If an AE on Day 1 occurs before IMP intake, it will be recorded as a pre-treatment AE. An AE that occurs after the first dose of the open-label period will be considered a TEAE for the open-label period.

If causality is missing, the AE will be regarded as being reasonably possibly related to IMP. Related AEs (judged as being reasonably possibly related to IMP) will be termed adverse drug reactions (ADR).

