10.2.2 Incidence of Adverse Events

The summaries will include the total number of subjects reporting an AE, the percentage of subjects (%) with an AE, and the number of events (E) reported. AEs will be presented by SOC sorted alphabetically and PT sorted in decreasing frequency of occurrence.

Summary tables will be prepared for:

- Any TEAEs
- Common TEAEs, defined as TEAEs with an incidence $\geq 2\%$ of subjects in any treatment group
- Any TEAEs by causality (related/unrelated)
- Any TEAEs by intensity
- Any AEs leading to death
- Serious adverse events
- Any TEAEs leading to discontinuation

Supporting data listings will be provided for:

- All adverse events sorted by trial site and subject ID
- All adverse events sorted by MedDRA SOC and PT
- Serious adverse events
- Adverse events leading to death
- Adverse events leading to discontinuation

A listing of SOC and PT for all unique verbatim will be provided.

For the open-label period, the following summaries and listings will be provided for subjects who receive the open-label treatment:

- Any TEAEs
- Any TEAEs by causality (related/unrelated)
- Any TEAEs by intensity
- Any AEs leading to death
- Serious adverse events
- Any TEAEs leading to discontinuation

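### A pre-treatment AE that becomes milder after dosing is recorded again with a post-dose onset and so counts as a treatment-emergent AE

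*Protocol*

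**What the plan says.** **Recording.** The general rule in Protocol 8.2.2 (Adverse Events) is one record per AE: when intensity changes, "a worst-case approach should be used when recording the event, i.e. the highest intensity and the longest duration of the event". Footnote a makes an exception for an AE with onset before the first IMP administration. If such an AE "changes in intensity, this must be recorded as 2 separate events". The first record is closed at the change, and "The second AE should be recorded with date and time of onset when the intensity changed".

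**Counting.** SAP 10.2 states: "A 'pre-treatment' AE will be defined as an AE that occurs between screening and the first dose of the IMP". A TEAE "will be an AE which occurs in the time interval from initial dosing (IMP intake) to the end of treatment visit". Protocol 9.8.2 defines a TEAE in the same timing-only way.

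**Synopsis.** The safety paragraph of the protocol synopsis has two limbs joined by *or*: any AE occurring after the start of IMP, or a "pre-existing medical condition that worsens in intensity after the start of IMP". The worsening limb does not appear in Protocol 9.8.2 or SAP 10.2.

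**Use.** Incidence and severity of AEs is a listed secondary endpoint (Protocol 2.2, SAP 2.2.3). TEAEs are tabulated overall, by intensity and by causality (SAP 10.2.1 and 10.2.2).

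**The concern.** Footnote a turns on a change of intensity in either direction. When the change is an improvement after dosing, the site must open a second record whose only onset date is post-dose. The counting rule looks only at timing, does not link the two records and does not ask whether the event got worse. A partial recovery is therefore tabulated as a new event on treatment, with its own intensity and causality rating.

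The situation is plausible. AEs are collected from consent (Table 1, note e), and screening may last up to 21 days. It includes medication washout and an endoscopy 4 to 10 days before randomization (Protocol 6.2.1), so some AEs may still be present on Day 1. What is at stake is the accuracy of the TEAE tables for a named secondary endpoint.

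**Working it through.** The plan gives no figure on this point, so the check is to apply the recording rule and then the counting rule to each course that a pre-treatment AE can take.

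| Course of the pre-treatment AE | Records under footnote a | Class under SAP 10.2 and Protocol 9.8.2 | Class if the second record must be more intense |
|---|---|---|---|
| Moderate before dosing, severe after | Two; second onset post-dose | Second record is a TEAE | TEAE |
| Moderate before dosing, mild after | Two; second onset post-dose | Second record is a TEAE | Not a TEAE |
| Intensity unchanged | One; pre-dose onset | Pre-treatment | Pre-treatment |
| Intensity changes before the first dose | Two; both onsets pre-dose | Both pre-treatment | Both pre-treatment |

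Only the second row goes wrong, and it is the only row that the proposed condition alters.

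**Is the split needed for improvement?** No. Without the footnote, the worst-case rule would keep one record with the pre-dose onset and the highest intensity. For a step-down, that is moderate with a pre-dose onset, which is correct. For a post-dose worsening, the same rule would give a severe event with a pre-dose onset, and the worsening would be missed. The exception is needed for that case alone.

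**Does any other text remove the record?** The SAP says that the AE occurs in the interval and does not use the word onset. But the second record has no date before dosing, and no rule ties it to the earlier one. Under the synopsis it fails the worsening limb but meets the other limb, because as recorded it is an AE occurring after the start of IMP. All three definitions let it through.

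**Scale.** The documents give no rate for AEs carried into Day 1 or for step-downs. As an illustration only, assume that 5% to 10% of subjects carry an AE into Day 1 and that 20% to 40% of those step down after dosing. With the planned 110 per arm:

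- low end: 110 × 0.05 × 0.20 = 1.1 subjects per arm;
- high end: 110 × 0.10 × 0.40 = 4.4 subjects per arm.

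These are subjects with at least one such record, over all preferred terms. The rise in the any-TEAE count would be smaller, because some of them would have another TEAE anyway.

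**The case against.** The best defence is that the footnote was plainly written to catch post-dose worsening, since it is an exception to a worst-case rule that a step-down never disturbs. Sites may apply it that way. AE summaries are descriptive, no test or decision rule depends on them, and all AEs are listed by site and subject, so a reader could find the pairs. This stands as to consequence. It does not stand as to the rule: the footnote says *must*, gives no direction, and no written instruction tells anyone to drop the second record.

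A reader might also infer four stronger points, which the documents do not support:

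- **That the drug would be penalised because it relieves symptoms.** Protocol 8.1 records findings from screening assessments as medical history, not AEs, and stool frequency and rectal bleeding are assessed at Visit 0. The symptoms that the drug targets are therefore largely outside the pool of pre-treatment AEs. Without evidence that step-downs differ between arms, similar noise in both is the reasonable expectation.
- **That the synopsis already has the right rule and the SAP chose the wrong one.** The synopsis's first limb captures the split record too, so the worsening condition would be a new rule in all three places.
- **That the common-TEAE list would be distorted.** SAP 10.2.2 has "Common TEAEs, defined as TEAEs with an incidence" of at least 2% in any group, presented by preferred term. Since 2/110 = 1.8% and 3/110 = 2.7%, these records alone would have to supply three of the same term in one arm. If the illustrative maximum of 4.4 were spread evenly over five terms (4.4/5 = 0.88 each), the Poisson chance of three or more is 1 − e^(−0.88) × (1 + 0.88 + 0.88²/2) ≈ 6% per term. Over ten terms (0.44 each) it is about 1%. A term already near the cut could be tipped over, but nothing shows that this is likely.
- **That drug-related events would be inflated.** SAP 10.2 does say "If causality is missing, the AE will be regarded as being reasonably possibly related to IMP". But a resolving pre-dose event becomes an adverse drug reaction only if the investigator rates it as reasonably possibly related or leaves causality blank. Neither is the expected course.

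**Conclusion.** Wrong as written, with low consequence. On the literal text, a pre-treatment AE that becomes milder after dosing is counted as a TEAE, and nothing in the protocol or SAP prevents it. This follows from the wording alone and needs no assumption about rates.

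The consequence is a small inflation of the descriptive any-TEAE, by-intensity and by-causality tables. Its size is unknown: the range of about 1 to 4 subjects per arm rests wholly on assumed rates. A difference between arms is not shown, and no efficacy analysis is touched.

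**What to change.** 1. In SAP 10.2 and Protocol 9.8.2, and in the synopsis for consistency, state that the second record of a split pre-treatment AE is treatment-emergent only if its intensity is higher than that of the linked pre-dose record. True worsenings remain TEAEs.
2. Identify the pairs before unblinding: same subject, same preferred term, and the first record's outcome date equal to the second record's onset date. Footnote a itself places both dates at the intensity change. Do not rely on the outcome category, because the label in footnote a (*not yet recovered*) is not among the outcomes listed in 8.2.2, which has *not recovered*.
3. If sites are still recording, replace *changes* with *worsens* in the trigger of footnote a, so that improvements stay in one record.

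The cost is one sentence in each of three places, one derivation from fields already collected, a blinded check of what should be a few pairs, and an optional one-word change to the footnote. No new data are needed.

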### **Intensity**

The intensity of an AE must be classified using the following 3-point scale:

Mild: awareness of signs or symptoms, but no disruption of usual activity

Moderate: event sufficient to affect usual activity (disturbing)

Severe: inability to work or perform usual activities (unacceptable)

### **Causal Relationship to IMP**

The possibility of whether the IMP caused the AE must be classified as 1 of the following:

Reasonable possibility: There is evidence or argument to suggest a causal relationship between the IMP and the AE. The AE may occur as part of the pharmacological action of the IMP or may be unpredictable in its occurrence.

Examples:

- AEs that are uncommon but are known to be strongly associated with IMP exposure
- AEs that are not commonly associated with IMP exposure, but the event occurs in association with other factors strongly suggesting causation, such as a strong temporal association or the event recurs on rechallenge

No reasonable possibility: There is no reasonable evidence or argument to suggest a causal relationship between the IMP and the AE.

Examples:

- known consequences of the underlying disease or condition under investigation
- AEs common in the trial population, which are also anticipated to occur with some frequency during the course of the trial, regardless of IMP exposure

### **Action Taken with IMP**

The action taken with the IMP in response to an AE must be classified as 1 of the following:

- no change (medication schedule maintained or no action taken)
- withdrawn

- interrupted

### **Other Action Taken**

Adverse events requiring therapy must be treated with recognized standards of medical care to protect the health and well-being of the subject. Appropriate resuscitation equipment and medicines must be available to ensure the best possible treatment of an emergency situation.

If medication is administered to treat the AE, this medication should be entered in the concomitant medication log.

### **Date of Outcome**

The date and time (time can be deleted/omitted, if applicable) the subject recovered or died will be recorded.

### **Outcome**

The outcome of an AE must be classified as 1 of the following:

- recovered (fully recovered or the condition has returned to the level observed at initiation of trial treatment)
- recovered with sequelae (resulted in persistent or significant disability/incapacity)
- recovering
- not recovered
- fatal

### **8.3 Pregnancy and Pregnancy Outcome**

Every effort must be made to avoid pregnancy during the trial. If a pregnancy occurs, the IMP should be immediately stopped and Global Pharmacovigilance at Ferring Pharmaceuticals must be informed using the Pregnancy Report Form within 3 calendar days. Note that pregnancy itself is not a serious adverse event (SAE). The mother and the fetus must be followed at least until the birth of the infant and 1 month after the birth of the infant. In general, the follow-up will include the course, duration, and the outcome of the pregnancy as well as neonatal health. If a pregnancy results in an abnormal outcome (birth defect/congenital anomaly), this must be reported as an SAE to Global Pharmacovigilance at Ferring Pharmaceuticals, as described in Section 8.4.2. Any abnormal pregnancy outcome that the investigator and/or sponsor consider to be related to the IMP will be treated as an expedited report.

## 8.4 Serious Adverse Events

### 8.4.1 Serious Adverse Event Definition

Serious AEs are defined as follows:

An event is defined a serious adverse event if it:	Guidance
results in death	Any event resulting in a fatal outcome must be fully documented and reported, including deaths occurring within 4 weeks after the treatment ends and irrespective of the causal relationship to the IMP. The death of a subject enrolled in a trial is per se not an event, but an outcome.
is life-threatening	The term life-threatening refers to an AE in which the subject was at immediate risk of death at the time of the event. It does not refer to an event, which may have caused death if it were more severe.
requires in-patient hospitalization or prolongation of existing hospitalization	The term hospitalization means that the subject was admitted to hospital or that existing hospitalization was extended as a result of an event. Hospitalization describes a period of at least 24 hours. Overnight stay for observation, stay at emergency room, or treatment on an outpatient basis do not constitute a hospitalization. However, medical judgment must always be exercised and, when in doubt the case should be considered serious (i.e., if case fulfils the criterion for a medically important event). Hospitalizations for administrative or social purposes do not constitute SAEs. Hospital admissions and/or surgical operations planned before trial inclusion are not considered AEs, if the illness or disease existed before the subject was enrolled in the trial, provided that the condition did not deteriorate during the trial.
results in persistent or significant disability/incapacity	Disability/incapacity means a substantial disruption of a person's ability to conduct normal life functions. In doubt, the decision should be left to medical judgment by the investigator.
is a congenital anomaly/birth defect	Congenital anomaly/birth defect observed in any offspring of the subject conceived during treatment with the IMP.
is an important medical event	
Important medical events are events that may not be immediately life-threatening or result in death or hospitalization but may jeopardize the subject or may require intervention to prevent 1 of the other outcomes listed in the definition above. Examples of important medical events include AEs that suggest a significant hazard, contraindication or precaution, occurrence of malignancy, or development of drug dependency or drug abuse. Medical and scientific judgment should be exercised in deciding whether events qualify as medically important.
 
Important medical events include any suspected transmission of an infectious agent via a medicinal product. Any organism virus or infectious particle (e.g., prion protein transmitting transmissible spongiform encephalopathy), pathogenic or non-pathogenic, is considered an infectious agent. A transmission of an infectious agent may be suspected from clinical symptoms or laboratory findings indicating an infection in a subject exposed to a medicinal product.

## 8.4.2 Collection, Recording and Reporting of Serious Adverse Events

### SAE Reporting by the Investigator

All SAEs must be reported **immediately** to Global Pharmacovigilance at Ferring Pharmaceuticals as soon as it becomes known to the investigator and not later than within 24 hours of his/her knowledge of the occurrence of an SAE. The investigator is responsible for submitting the completed paper SAE report form with the fullest possible details **within 3 calendar days** of his/her knowledge of the SAE.

The SAE must be included in the eCRF system. In addition, a paper SAE report must be completed and submitted according to the instructions provided on the form and sent to Global Pharmacovigilance at Ferring Pharmaceuticals using the contact details below.

Global Pharmacovigilance, Ferring Pharmaceuticals A/S

E-mail: [REDACTED]

Fax: [REDACTED]

eCRF information regarding demographics, AEs, medical history, and concomitant medication is **mandatory** for initial reports and for follow-up reports if any changes have been made since the initial report.

Additional information relevant to the SAE, such as hospital records, results from investigations (e.g., laboratory parameters that are not already uploaded in the eCRF, invasive procedures, scans, x-rays, and autopsy results) can be faxed or scanned and e-mailed to Ferring Global Pharmacovigilance using the contact details in the section above. In any case this information must be supplied by the investigator upon request from Ferring. On any copies provided, such details such as subject's name, address, and hospital ID number should be concealed, and subject number should be provided instead.

The investigator will supply Ferring and the IEC/IRB with any additional requested information, such as results of post-mortem examinations and hospital records.

### Expedited Reporting by Ferring

Ferring will report all AEs that are **serious, unexpected, and with a reasonable possible causality to the IMP** as judged by either the investigator or Ferring to the relevant parties within the stipulated timelines. The expectedness of events will be assessed by Ferring according to the Investigator's Brochure.

SAEs will be considered reportable regardless of whether the IMP was used in accordance with the provisions in the protocol, Investigator's Brochure, and labelling.

## **8.5 Follow-up of Adverse Events and Serious Adverse Events**

### **8.5.1 Follow-up of Adverse Events with Onset during the Trial**

During the trial, the investigator must follow each AE until it is resolved or until the medical condition of the subject is stable.

After the subject's last visit, the investigator must follow-up on any AE classified as serious or considered to have a reasonable possible causality to the IMP until it is resolved or until the medical condition of the subject is stable. All such relevant follow-up information must be reported to Ferring. If the event is a chronic condition, the investigator and Ferring may agree that further follow-up is not required.

### **8.5.2 Collection of Serious Adverse Events with Onset after Last Trial Visit**

If an investigator becomes aware of an SAE after the subject's last visit, and he/she assesses the SAE to have a reasonable possible causality to the IMP, the case will have to be reported to Ferring, regardless how long after the end of the trial this takes place.

## 9 STATISTICAL METHODS

All analyses will be detailed in a subsequent statistical analysis plan.

### 9.1 Determination of Sample Size

The true remission rates at Week 8 for mesalamine 4 g extended release granules (sachet) and placebo regimens were assumed as 36% and 18%, respectively, based on Kamm (2007) (3), Lichtenstein (2007) (4), and Marteau (2005).(5) Under these assumptions, a sample size of 110 randomized subjects per group will provide at least 85% power to detect a statistically significant treatment group difference in the remission rate at a two-sided 0.05 significance level using the chi-square test.

### 9.2 Subject Disposition

The number of screened subjects will be summarized, and for subjects not randomized, the primary reason for exclusion from randomization will be summarized.

The number and percentage of subjects who are randomized, are treated with IMP, prematurely discontinued, and completed the double-blind period of the trial will be summarized with the reason of premature discontinuations. Similar summaries will be made for subjects who are enrolled to the 8-week open-label period.

The time to discontinuation will be summarized by the Kaplan-Meier estimates, and the treatment group difference will be tested by the log-rank test. In addition, reason-specific discontinuation will be summarized by the cumulative incidence estimates.

